### **6.3.3 Day 2**

- Subjects will take dexamethasone 8 mg PO twice a day

### **6.3.4 Day 3 (Window +1 Day) of Cycles 1, 2, and 4 Only**

- ECG in triplicate ([Section 7.2.4](#))
- Blood sample for PK for Cycles 1 and 2 only – omitted for retreatment subjects

### **6.3.5 Days 8 and 15 ( $\pm 2$ Days) and 29 ( $\pm 3$ Days)**

- Physical examination ([Section 7.2.1](#))
- Vital signs ([Section 7.2.2](#))

- PRO questionnaires EORTC QLQ-C30 and EQ-5D-5L – for subjects in Part B of the study only; to occur at screening, Cycle 2 (Days 1 and 29), and EOT ([Section 7.3.2](#))
- CBC ([Section 7.2.3](#))
- Serum chemistries ([Section 7.2.3](#))
- Urinalysis ([Section 7.2.3](#))
- Fluid retention questionnaire ([Section 7.2.7](#))
- Blood sample for PK for Cycles 1 and 2 only – omitted for retreatment subjects

In Cycles 5 and higher, the Day 8 visit may be reduced to a virtual visit consisting only of the Fluid retention questionnaire (similar to visits on Days 22 and 36, [Section 6.3.6](#)), but only if the previous 4 consecutive cycles lacked any clinically significant AEs. Visits on Days 15 and 29 must consist of all above procedures in all cycles.

### **6.3.6 Days 22 ( $\pm$ 2 Days) and 36 ( $\pm$ 3 Days)**

- Fluid retention questionnaire ([Section 7.2.7](#)) – may be conducted virtually

### **6.3.7 Disease Assessment**

- Disease assessment consists of CT scans of the chest, abdomen, and pelvis (and neck if indicated; [Section 7.3](#)). Tumor response will be assessed every 6 weeks counting from Cycle 1 Day 1, preferably before each dosing if possible, until 24 weeks, then every 12 weeks, thereafter.
- MRI of the brain – if clinically indicated (e.g., if CNS progression has been documented previously). CT of the brain with intravenous contrast may be substituted at the discretion of the Investigator. CNS lesion will be assessed every 6 weeks counting from Cycle 1 Day 1, preferably before each dosing if possible, until 24 weeks, then every 12 weeks, thereafter.
- Prostate cancer subjects only: 99 mTc Bone Scintigraphy, will be assessed every 6 weeks counting from Cycle 1 Day 1, preferably before each dosing if possible, until 24 weeks, then every 12 weeks, thereafter ([Section 7.3](#)).

## **6.4 End-of-Treatment Visit**

The EOT visit occurs 42  $\pm$ 3 days after the last dose of study drug or within 7 days of documentation of the decision to discontinue treatment, whichever is later.

- Physical examination ([Section 7.2.1](#))
- Vital signs ([Section 7.2.2](#))
- PRO questionnaires EORTC QLQ-C30 and EQ-5D-5L – for subjects in Part B of the study only; to occur at screening, Cycle 2 (Days 1 and 29), and EOT ([Section 7.3.2](#))
- CBC ([Section 7.2.3](#))
- Serum chemistries ([Section 7.2.3](#))

- Coagulation tests (Section 7.2.3)
- Urinalysis (Section 7.2.3)
- Pregnancy test (Section 7.2.9) for women of child-bearing potential
- ECG in triplicate (Section 7.2.4)
- ECHO (Section 7.2.5) – The EOT ECHO should be conducted on EOT ( $\pm 3$  days) (Appendix 13.1).
- ECOG performance status (Appendix 13.3)
- Fluid retention questionnaire (Section 7.2.7)
- Disease assessment consisting of CT scans of the chest, abdomen, and pelvis (and neck if indicated) – may be omitted if a Disease/Response Assessment was performed within the last 6 weeks (Section 7.3)
- MRI of the brain – if clinically indicated (e.g., if CNS progression has been documented previously); may be omitted if a Disease/Response Assessment was performed within the last 6 weeks. CT of the brain with intravenous contrast may be substituted at the discretion of the Investigator.
- Blood sample for PK
- Blood sample for ATA
- (Optional) fresh tumor tissue, collected at PD (Section 7.3)
- Blood inflammatory markers (Section 7.5.2)
- Blood tumor markers (Section 7.5.3)
- Soluble biomarkers (Section 7.5.4)
- CTCs (Section 7.5.5)
- Prostate cancer subjects only: 99mTc Bone Scintigraphy – may be omitted if performed within the last 6 weeks (Section 7.3)

### **6.5 Long-Term Follow-up (LTFU; Every 6 to 12 Weeks $\pm 1$ Week)**

For all subjects without PD (including those who discontinue study treatment for reasons other than PD), the first follow-up visit will occur at 6 weeks ( $\pm 1$  week) after the last dose of study drug, then every 6 weeks ( $\pm 1$  week) until 6 months, then every 12 weeks ( $\pm 1$  week), consisting of:

- Disease assessment consisting of CT scans of the chest, abdomen, and pelvis (and neck if indicated; Section 7.3)
- MRI of the brain – if clinically indicated (e.g., if CNS progression has been documented previously). CT of the brain with intravenous contrast may be substituted at the discretion of the Investigator.
- Blood tumor markers (Section 7.5.3)
- Circulating tumor cells (Section 7.5.5)

- Prostate cancer subjects only: 99mTc Bone Scintigraphy ([Section 7.3](#))
- Survival status

At progression, an optional collection of fresh tumor tissue may be conducted ([Section 7.3](#)).

After PD, subjects who are not retreated will be followed for subsequent anticancer therapies and dates, as well as survival status, similarly every 6 weeks ( $\pm 1$  week) until 6 months, then every 12 weeks ( $\pm 1$  week).

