### **Part A Dose Escalation**

Rovalpituzumab tesirine will be initially administered on Day 1 of each 6-week cycle, following a standard 3+3 dose-escalation approach. For each cohort in Part A, dose escalation is planned to proceed until a single maximum tolerated dose (MTD) (dose level and dosing interval inclusive) is determined.

The SMC will monitor the safety of the trial and may make dose-escalation and dosing-interval recommendations. The SMC may also recommend further evaluation of the safety at a given dose, investigation of alternative dose regimens (including a dose level that is intermediate to the planned dose levels), modification of the dosing interval, or limitation to the maximum number of doses. For instance, based on dose-limiting toxicities (DLTs) and/or adverse event (AE)-related dose delays, enrollment may change at the same dose to a different dosing schedule (e.g., up to 12-week cycles, in which rovalpituzumab tesirine is administered on Day 1 of each cycle of up to 84 days). The SMC may also recommend the elimination or cancellation of a dose level(s) in a cohort based on the experience in other cohorts. For instance, if 3 or more initially-enrolled cohorts establish the same dose level as MTD, the remaining cohorts may forgo escalation to higher dose levels.

Response will be assessed by radiographic imaging at protocol-specified time points determined by the subject's dosing schedule. In the 6-week cycle schedule, response assessments will be conducted between Days 36–42 of Cycles 1–4, and every 2 cycles thereafter. Prostate cancer-specific assessments are described in [Appendix 13.6](#).

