Tumor response will be assessed every 6 weeks during active study treatment until 24 weeks, and then every 12 weeks thereafter. Treatment decisions by the Investigator will be based on RECIST v1.1 (and/or PCWG3 for prostate cancer; [Appendix 13.7](#)).

Subjects will be eligible to continue treatment until unacceptable toxicity, disease progression (PD), withdrawal of consent, study termination, or completion of a planned course of treatment (if a regimen with a limited number of doses is selected), whichever occurs first. Subjects who discontinue study treatment prior to PD will be evaluated for response every 6 weeks until 24 weeks, then every 12 weeks until PD or initiation of new anticancer treatment, whichever occurs first, and will afterwards be followed for survival until death or study termination, whichever occurs first. [Appendix 13.7](#) includes specific additional guidance for prostate cancer subjects.

Blood samples for PK, immunogenicity, biomarker and pharmacodynamics assessments will be collected at protocol-defined time points to support the study endpoints ([Sections 7.4](#) and [7.5](#)).

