#### **5.2.4.1 Dose Holds or Delays**

Subjects who experience DLT in Cycle 1 should not receive further treatment with study drug unless clinical benefit is demonstrated with adequately managed toxicity and there is approval from the Medical Monitor and/or Sponsor. The subsequent dose level will be defined by the Medical Monitor and/or Sponsor in discussion with the site Investigator in the context of the type of AE observed.

If a subject has a clinically significant, unresolved AE on Day 1 of Cycle 2 or beyond, the start of the cycle may be delayed for up to 12 weeks. Longer dose delays may be permitted with the approval of the Medical Monitor if there was no documented PD. The AE must resolve to baseline or  $\leq$ Grade 1 prior to proceeding with treatment, unless the AE is determined to be clearly unrelated to study drug, or toxicity has been adequately managed.

Serosal effusions (e.g., pleural, pericardial, or ascites) that have been drained should remain stable or improved for at least 2 weeks prior to resumption of dosing (refer to [Table 5-1](#), below).

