#### **10.3.5 Analysis of Secondary Efficacy Endpoints**

The analysis of the secondary efficacy endpoints will be conducted using data from the Full Analysis set.

Burden of disease will be analyzed in a way similar to the analysis of the best ORR (described in the previous section).

DOR will be summarized for responders (*i.e.*, subjects with CR or PR only) by disease and cohort. PFS and OS will be summarized by disease and cohort. The PFS rate at additional time points may also be evaluated (e.g., 26, 39 and 52 weeks). DOR, and PFS, will be obtained by using the Kaplan-Meier approach similar to OS described in the previous section.

Details of the analysis of secondary efficacy endpoints will be described in the Statistical Analysis Plans.

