### **13. Appendices**

### 13.1 Schedule of Assessments

	Window	Screening 		Treatment (Each Cycle)							EOT 	LTFU				
		Day -15 to -1	Day -1	Day 1 	Day 2	Day 3 	Day 8 	Day 15	Day 22	Day 29			Day 36			
		-	-	±2 d	-	+1 d	±2 d	±2 d	±2 d	±3 d	±3 d	±3 d	42 days (6 weeks) after last dose	±3 d	Every 6-12 weeks thru 4 years 	
Location		X		X		X		X		X						
	Clinic Visit	X		X		X		X		X						
	Virtual Visit				X						X					
	Investigator (MD) present 	X		X				X								
Screening, Baseline, and Safety Assessments	Informed Consent	X														
	Demographics	X														
	Inclusion/Exclusion Criteria	X														
	Medical and Surgical History 	X														
	Malignancy History 	X														
	Prior Anticancer Treatments 	X														
	Physical examination	X		X				X				X				
	Vital Signs 	X		See 13.2				X				X				
	Height	X														
	Complete Blood Count 	X		X				X				X				
	Chemistries 	X		X				X				X				
	Coagulation Tests 	X		X												
	Urinalysis 	X		X								X				
Hepatitis B and C tests 	X															
Pregnancy Test 	X		X											X		
Electrocardiogram (ECG) 	X		See 13.2		X									X		
Echocardiogram 	X		X											X		
Performance Status (ECOG)	X		X											X		

	Screening 	Treatment (Each Cycle)							EOT 	LTFU					
		Day -15 to -1	Day -1	Day 1 	Day 2	Day 3 	Day 8 	Day 15			Day 22	Day 29	Day 36		
		Window	-	-	±2 d	-	+1 d	±2 d	±2 d	±3 d	±3 d	±3 d	±3 d	42 days (6 weeks) after last dose	Every 6-12 weeks thru 4 years 
		Fluid Retention Questionnaire 			X			X	X	X	X	X	X	X	
		Daily Weight Diary 													
		Adverse Events													
		Concomitant Medications 													
Treatment		Rovalpituzumab tesirine			X										
		Dexamethasone		X											
Response Assessment	X	Disease/Response Assessment 				Subjects will be assessed for response every 6 weeks (± 1 week) counting from CID1 until week 24, and then every 12 weeks thereafter (± 1 week)									
	X	MRI of the Brain 				CNS lesions will be assessed every 6 weeks (± 1 week) counting from Cycle 1 Day 1 until week 24, then every 12 weeks, thereafter (± 1 week). 									

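### Tumor scans are timed from three different origins, so recorded PFS and DOR can shift with dose delays and treatment stops

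*Combined protocol and SAP*

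**What the plan says.** Four sets of instructions stand in the current text.

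- **By cycle.** The synopsis paragraph on Part A ties imaging to "protocol-specified time points determined by the subject's dosing schedule", and for 6-week cycles specifies that "response assessments will be conducted between Days 36–42 of Cycles 1–4, and every 2 cycles thereafter". The Part B paragraph also refers to the dosing schedule, then gives a 6-week interval to week 24 and a 12-week interval after that.
- **By weeks from Cycle 1 Day 1 (C1D1).** Section 6.3.7: "Tumor response will be assessed every 6 weeks counting from Cycle 1 Day 1, preferably before each dosing if possible, until 24 weeks". After that point its interval is 12 weeks. Appendix 13.1 has the same origin, with scans every 6 weeks "until week 24, and then every 12 weeks thereafter".
- **By weeks from the last dose.** Section 6.5 covers all subjects without progression, including those who stopped treatment for another reason. It says "the first follow-up visit will occur at 6 weeks" after the last dose, then every 6 weeks until 6 months, then every 12 weeks. These visits include CT.
- **No stated origin.** Section 3.1: "Subjects who discontinue study treatment prior to PD will be evaluated for response every 6 weeks until 24 weeks, then every 12 weeks". Footnote 6 of Appendix 13.1 changes the interval at 6 months. Neither says from when, and Section 6.5 does not say where its 6 months starts.

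Section 5.2.4.1 provides that "the start of the cycle may be delayed for up to 12 weeks", or longer with approval. The synopsis allows cycles of up to 84 days, and Part B may use a finite number of doses. PFS and DOR are Kaplan-Meier summaries (synopsis; Section 10.3.5). PFS status at 6 months is an endpoint (Section 2.4.2), and PFS rates at 26, 39 and 52 weeks are named as examples (Section 10.3.5).

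**The concern.** Radiographic progression is found at a scan, so the recorded date depends on when scans are taken. If the scan dates move with a dose delay or with the last dose, recorded PFS and DOR move too, even when tumor growth is the same. Delays come largely from toxicity, and the number of doses may differ between Part B regimens. Differences between cohorts, regimens or sites in a median or landmark rate could then partly reflect the scan calendar. The sections reviewed give no analysis rule for uneven scan intervals; details of the secondary endpoints are left to a later SAP. Analysis cannot fully recover a progression date that no scan was scheduled to catch.

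**Working it through.** The plan states no figure that rests on scan timing, so there is nothing of its own to reproduce. The check lists the nominal scan weeks under each rule, then reads off what would be recorded.

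**Step 1. Nominal scan weeks.** Inputs: the schedules above, 6-week cycles, and a delay before Cycle 2 within the permitted 12 weeks.

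| Situation | C1D1 | Cycle | Last dose |
|---|---|---|---|
| No delay, treatment continues | 6, 12, 18, 24, 36, 48 | 6, 12, 18, 24, 36, 48 | not in use |
| 3-week delay | unchanged | 6, 15, 21, 27, 39 | after dose 2 (week 9): 6, 15, 21, 27, 33, 45 |
| 6-week delay | unchanged | 6, 18, 24, 30, 42 | not calculated |
| 12-week delay | unchanged | 6, 24, 30, 36, 48 | see fix |
| No delay, stop after dose 2 (week 6) | unchanged | not in use | 6, 12, 18, 24, 30, 42, 54 |

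The last-dose column counts 6 months from the last dose. Counted from C1D1, the last row becomes 6, 12, 18, 24, 36, 48, the same as the C1D1 schedule. The 3-week-delay entry becomes 6, 15, 21, 33, 45, which still differs. For cycles longer than 6 weeks the synopsis gives no scan days, only the link to dosing.

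**Step 2. Effect on a single date.** True progression at week 7 is recorded at week 12 (C1D1), week 18 (cycle schedule, 6-week delay) or week 24 (cycle schedule, 12-week delay). The 12-week delay opens an 18-week gap between scans, weeks 6 to 24.

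**Step 3. Effect on summaries.** Assumption: exponential PFS with a median of 3.9 months, the value Section 1.2 quotes for small cell lung cancer, or 3.9 × 4.345 = 16.9 weeks (16.95 in the calculation). The true proportion progression-free at week t is S(t) = 2^(−t/16.95). The recorded PFS rate at week L is S at the last scan on or before L. The recorded median is the first scan at which S is 50% or less. Every subject is given the same 3-week delay before Cycle 2.

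- True 26-week PFS: 2^(−26/16.95) = 34.5%.
- C1D1 schedule: last scan by week 26 is week 24, so 2^(−24/16.95) = 37.5%. S(12) = 61.2% and S(18) = 47.9%, so the recorded median is week 18.
- Cycle schedule, or last-dose schedule after dose 2: last scan is week 21, so 2^(−21/16.95) = 42.4%. S(15) = 54.1% and S(21) = 42.4%, so the recorded median is week 21.

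At this median, neither delayed figure changes if 6 months is counted from C1D1, or if a week-12 scan is added for the subject whose last dose was at week 9.

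**Step 4. Sensitivity to the assumed median.** 3-week delay on the cycle schedule, against C1D1:

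| True median | 26-week PFS, delayed / C1D1 | Recorded median week, delayed / C1D1 |
|---|---|---|
| 2.5 months | 26.2% / 21.6% | 15 / 12 |
| 3.9 months | 42.4% / 37.5% | 21 / 18 |
| 6 months | 57.2% / 52.8% | 27 / 36 |

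The 26-week shift stays near 5 points, but the median moves in either direction. Across the delays and stops tried, the recorded median moved by 0 to 12 weeks.

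**Step 5. Where the shift is zero.** With a 12-week delay on the cycle schedule, the last scans before weeks 26, 39 and 52 are weeks 24, 36 and 48, as on the C1D1 schedule. All three landmark rates are unchanged (37.5%, 22.9%, 14.0%), although the recorded median is week 24 against 18.

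The calculation omits visit windows, unscheduled scans and deaths between scans. No figure was calculated for DOR.

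**The case against.** The by-cycle timing appears only in the synopsis and looks like a leftover. Version 4.0 lists clarifying the response assessment schedule among its purposes, and sites work from Section 6 and Appendix 13.1. Section 6.3.7 sits under the treatment period and Section 6.5 is follow-up, so those two can be read as successive phases. The end-of-treatment scan (Section 6.4) and the confirmatory scans (Section 7.3) close some of the modelled gaps, especially for responders. Primary interest is in safety, and no test rests on PFS or DOR.

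Much of this stands, and it rules out several stronger readings that a reader might infer:

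- That the schedules agree only with no delay and no early stop, so that no site could follow them all. The documents do not establish this. If 6 months runs from C1D1, an undelayed early stop gives the same scan weeks, and the phase reading lets a site follow Sections 6.3.7 and 6.5 in turn.
- That stopping after a week-6 dose moves 39-week PFS from about 23% to 29%. This appears only if 6 months is counted from the last dose, which the text does not say.
- That a 12-week delay inflates PFS from about 61% to 78%. That contrast is at week 12, not one of the protocol's landmarks; at the named landmarks the same example shows no change.

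What remains is that the synopsis is current text, that Appendix 13.1 does not clearly confine the C1D1 schedule to treatment, and that a switch of origin at the last dose itself ties scan dates to when treatment stops.

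**Conclusion.** The point holds as an inconsistency of origin, with a modest and variable effect. After delays, and after early stops on one reading of 6 months, the schedules separate and recorded PFS and DOR shift with treatment timing; longer cycles leave the cycle-based dates unspecified. The illustrated size is about 5 percentage points at 26 weeks and 3 weeks in the median. It rests on exponential PFS, a median borrowed from another tumor type, and a 3-week delay in every subject, so a cohort with fewer delays would show less. The direction is not fixed. This is worth correcting but is not a flaw in the trial's decision rules: the endpoints are secondary and descriptive, and the response-rate sample size (Section 10.1) and futility figures (Section 10.3.6) do not use scan timing.

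**What to change.** Use one imaging schedule for all subjects: weeks from C1D1, as already in Section 6.3.7 and Appendix 13.1, on or off treatment and whatever the dose delays, until progression or new anticancer therapy. Align five places with it: the synopsis paragraphs on Part A and Part B, Section 3.1, Section 6.5, and footnote 6 of Appendix 13.1. State the origin of 24 weeks and 6 months wherever they appear. Keep last-dose timing only for non-imaging contacts. Leave the end-of-treatment and confirmatory scan requirements as they are.

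The cost is wording plus a few changed scans. Some off-treatment scans move or drop out: on the last-dose reading, a subject stopping after an undelayed dose 4 (week 18), or after a dose 2 delayed by 12 weeks (also week 18), has scans at weeks 30, 36, 42 and 54, against weeks 36 and 48 over the same period. A delayed subject may have one more scan than on the cycle schedule: with a 12-week delay, six by week 48 (6, 12, 18, 24, 36, 48) instead of five (6, 24, 30, 36, 48).

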## **6.6 End of Study/End of Follow-Up**

The date the subject met criteria for study discontinuation and the reason for study discontinuation will be recorded. Where available, subsequent anticancer therapies and dates, date of progression (if not already captured on study), and survival status will be recorded.

## 7. Study Assessments

### 7.1 Screening/Baseline Assessments

Only subjects who meet all inclusion and exclusion criteria specified in [Section 4](#) (and [Appendix 13.7](#), for prostate cancer subjects) will be enrolled in this study.

Absence of active CNS tumor or metastases will be confirmed by MRI of the brain. CT of the brain with intravenous contrast may be substituted at the discretion of the Investigator.

Demographics include age, gender, and race.

Subject medical history includes a thorough review of significant past medical history, current conditions, smoking history, any diagnosis and treatment for prior malignancies, including response to treatment, and any concomitant therapies.

Malignancy history should include tumor type, stage, grade and grading system, sites of metastases, and mutational status. The latter should include, at least, status of *BRAF* for melanoma subjects, and *RET* for MTC subjects.

Standard of Care procedures completed prior to the subject signing ICF, but within the study screening window, may be used as screening procedures.

#### 7.1.1 Central Immunohistochemistry Assessment

For all subjects, tumor tissue representative of the qualifying malignancy must be submitted to a central laboratory for determination of DLL3 expression. An archived tumor specimen, or a fresh specimen, obtained via on-study biopsy, may be used. DLL3 positivity, for purposes of eligibility, will be defined as staining in  $\geq 1\%$  tumor cells. The central assessment will be definitive regarding DLL3 expression, which will be relayed to the Investigator. All decisions regarding study eligibility will be based upon DLL3 expression adjudicated by this central assessment.

### 7.2 Safety Assessments

In addition to the surveillance and recording of AEs, the assessment of safety during the course of this study will consist of the recording of concomitant therapies, protocol-specified physical examination findings including vital signs, daily weight diary, ECOG performance status, disease assessments, and diagnostic testing (including laboratory testing, radiographic imaging, ECGs and ECHOs).

Safety will be monitored over the course of the study by an SMC.

